5 MYSTUDIES APP

5.1 Description of the MyStudies Mobile App

The FDA MyStudies App is designed to facilitate the input of real world data directly by patients which can be linked to electronic health data supporting traditional clinical trials, pragmatic trials, observational studies and registries. This platform has been developed under sponsorship of the FDA and private sector partners as open source software, enabling the app and associated data storage to be configured by organizations conducting clinical research according to their needs and utilizing their own branding.

All users of the MyStudies Mobile App will be asked to register for the app using a unique email address. The email address is used to confirm that the registrant is a real person. The user will receive a confirmation email with a confirmation code. The user will not be officially registered in the app until they enter the code in the app. This registration code is distinct from a patient token, which each subject will be provided by study staff for use in enrolling in the study. All users must consent to a study before completing any study surveys. The site maintains control of the release of patient tokens for the app and will only release them once the consent to participate has been signed by the parent/legal guardian.

Study participants may be alerted to new surveys by “push notifications.” A notification will pop up on their smart phone screen, telling them a new survey is available. Participants will be able to turn off notifications of new surveys at any time. The use of push notifications does not require any personal identifiers, such as a cell phone number.

5.2 Data Access Security and Storage

Data collected by the MyStudies mobile app will be transferred to and stored with the project vendor/collaborator LabKey.

All personal health information collected and stored on the LabKey platform for this study will be deleted from that platform within 60 days of completion of study data analysis, unless such data collection and usage subsequently becomes governed by another IRB-approved protocol, such as for the CARRA Registry.

Harvard Pilgrim Health Care Institute (HPHCI, the coordinating center for MyStudies mobile app, will use the platform hosted by LabKey Software, to provide a set of unique patient enrollment tokens for distribution to the study cohort. HPHCI will distribute these tokens to study site personnel, and study site personnel will assign and distribute a token to each participant as they identify and enroll them in the study cohort. Study personnel will maintain the linkage of token associations with participant identifiers.

Participants respond to questionnaires in the MyStudies mobile app at their convenience for as long they are available in the app. Data are stored locally on the app until the participant indicates they have completed the questionnaire or task by tapping “done” on the final screen. Data will be encrypted during transmission and in the LabKey Server. Participants can optionally use a Passcode/TouchID/FaceID (depending on phone capabilities) to prevent others who may be using their phone from accessing the MyStudies app.

Only designated staff at HPHCI will have access to patient-reported data captured by the MyStudies mobile app and housed within the LabKey platform. Designated CARRA Registry staff will have access to view and download MyStudies subject data, including individual-level data, and link individual-level data with other CARRA Registry data using MyStudies and CARRA Registry subject identifiers. The HPHCI designated staff may create data queries, review aggregated query results, and view individual-level data without otherwise downloading patient data.

5.3 Survey Distribution for Mobile App Users

Surveys will be distributed to app users who have consented to the study on the following schedule:

- **Study Arm 1 (Intervention group)**

- One question survey asking on what date the medication was last administered.
 - Schedule: Available immediately after enrollment in the study in the app
 - Duration: Available until completed by the patient
 - Other notes:
 - The response to this question will be used as the **anchor date** for the medication administration survey
- Covid-19 Survey
 - Schedule: Weekly, starting on **anchor date** + 1 week
 - Duration: Available for 12 months (48 weeks) based on enrollment date of patient in the app
- Medication Administration Survey
 - Schedule: Weekly, starting on **anchor date** + 1 week
 - Duration: Available for 48 weeks post enrollment
- Uveitis Survey
 - Schedule: Available continuously
 - Duration: Available for 12 months (48 weeks) based on enrollment date of patient in the app
 - Other notes:
 - Appointment dates do not need to be entered in the app.
 -

5.4 Survey Notifications

Participants may receive the following phone notifications when using the app to participate in this study.

- A new activity is available/an activity is about to expire
 - Text: A new run of the scheduled activity <activity name>, is now available and is valid until <Month, DD, YYYY TT>. Your participation is important. Please visit the study to complete it now.
- A one-time activity is starting
 - Text: The activity <activity name>, is now available to take. Please visit the study to complete it.

- New run of weekly/monthly existing activity
 - Text: A new run of the <weekly/monthly/ > activity <activity name>, is now available. Please visit the study to complete it.
- Weekly activity is set to expire
 - Text: The current run of the weekly activity <activity name>, will expire in 24 hours. Your participation is important. Please visit the study to complete it now.
- The study is paused via the WCP
 - Text: The study <study name > has been paused We will notify you when it is resumed.
- The study is resumed via the WCP
 - Text: The study <study name as given in WCP 50 char max> has been resumed. Visit the study to start participating in activities again.
- The study is close the study via the WCP
 - Text: The study <study name > has been closed. We thank you for your participation.
- A new resource has been added
 - Text: custom

6 CLINICAL TRIAL TREATMENT INTERVENTIONS

All eligible participants will be enrolled to receive treatment with 24-doses of weekly SQ abatacept (Orencia) plus usual care.

6.1 Abatacept (Orencia) – Study Drug

Participants enrolled to receive SQ abatacept (Orencia) will receive training and study materials (3 month or 6 month drug supply) on the day of enrollment. The first dose should be administered at the site or at home with telehealth guidance from the investigator or other study staff once all test results have been verified. All study participants enrolled will be trained by the study staff on study drug administration. A resupply of IP will occur at the three-month visit if a 6-month supply was not provided at enrollment.

The 50 mg, 87.5 mg and 125 mg SQ doses that are approved for use in pediatric patients in the United States will be supplied by a US-based depot. The 125 mg SQ dose approved for use in Canada will be sourced from a Canadian vendor.

6.2 Potential Benefits/Risks of Abatacept (Orencia)

The safety profile of abatacept (Orencia) is well-established, with infection (primarily upper respiratory tract) and injection site reactions most common.^{59, 60}

6.3 Storage

Study drug solution supplied in prefilled syringe should be refrigerated at 2°C to 8°C (36°F to 46°F). Do not use study drug beyond the expiration date on the prefilled syringe. Protect from light by storing in the original package until time of use. Do not allow the prefilled syringe to freeze.

6.4 Study Drug Discontinuation Criteria

Study participants who permanently stop study drug in Limit-JIA should be encouraged to continue in the study. If for any reason a study participant must permanently stop study drug, every effort should be made by the Site Investigator/staff to keep the study participant in the Limit-JIA study to collect important safety and clinical data.

Withdrawal from the Limit-JIA study does not automatically withdraw the study participant from the CARRA Registry.

Study participant must be permanently discontinued from the study drug if the following occurs:

- Positive urine pregnancy test
- Non-compliance with study drug. Study participants' compliance with study treatment will be assessed throughout the study. Participants who miss more than one dose should be re-educated on the requirement for treatment compliance. Every effort will be made to keep participants in the study and to re-educate those who continue to miss doses. Participants who continue to be non-compliant after multiple visit assessments may be permanently discontinued from study drug at the discretion of the Site Investigator after consultation with the sponsor.

- Non-compliance with weekly diary. Study participants' must complete their weekly electronic or paper diary between study visits. Participants who are non-compliant after multiple visit assessments may be permanently discontinued from study drug at the discretion of the Site Investigator after consultation with the sponsor.
- Serious Infection
- Physician discretion
- Achievement of any of the primary outcomes as defined in the protocol (disease extension, uveitis and/or need for escalation of systemic therapies)
- SAE attributed to abatacept
- AE attributed to abatacept that at the discretion of the site PI warrants drug discontinuation.
- Conversion to positive PPD or Quantiferon Gold assay result that occurs during the study (if tested as standard of care)

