6.4.2 Temporary Discontinuation of Study Drug

Abatacept can be temporarily held for a maximum of 2 weeks for significant viral infections or for bacterial infections requiring antibiotics. Patients may continue/resume study drug at discretion of physician. Temporary discontinuation of study drug for COVID-19 infection should be handled the same as temporary discontinuations for other viral infections. Study drug administration in COVID-19 positive patients will be handled per physician discretion, following CDC and American College of Rheumatology COVID-19 guidelines. With regards to vaccinations for COVID-19, administration of abatacept will follow the guidance set forth by the American College of Rheumatology to hold SQ abatacept one week prior and one week after the first COVID-19 vaccine dose (only). There is no interruption around the second vaccine dose.⁶⁸

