6.7 COVID-19 Guidance

The following strategies will be employed during the clinical trial to optimize participant safety:

- Provide a fact sheet to all screened subjects on the symptoms of COVID-19
- Administer a COVID-19 questionnaire related to exposure history and physical symptoms
- Obtain and document current temperature at screening and throughout study period. If a potential subject has a temperature greater than 100.4, the subject cannot be enrolled into the trial until they have been afebrile for at least 48 hours and had negative COVID-19 testing. Subjects who develop a fever during the trial will be instructed to follow-up with their local provider for consideration of COVID-19 testing.
- The re-start of study drug after COVID-19 infection is at the discretion of the PI, following ACR guidance.
- See Section 4.9 (Immunizations) and Section 6.4.2 (Temporary Discontinuation for Study Drug) for additional information on COVID-19 guidance

- The COVID-19 Vaccine Clinical Guidance Summary for Patients with Rheumatic and Musculoskeletal Diseases developed by the ACR COVID-19 Vaccine Clinical Guidance Task Force can be found at the following site:
<https://www.rheumatology.org/Portals/0/Files/COVID-19-Vaccine-Clinical-Guidance-Rheumatic-Diseases-Summary.pdf>

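### A serious infection, serious COVID-19 above all, falls under both a mandatory permanent stop of abatacept (6.4) and a discretionary restart (6.4.2, 6.7), and neither provision is said to prevail

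*Combined protocol and SAP*

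**What the plan says.** Section 6.4 of the protocol gives a list headed "Study participant must be permanently discontinued from the study drug if the following occurs". One item is "Serious Infection". It stands alone, with no definition, threshold, exception or cross-reference. A neighbouring item is "SAE attributed to abatacept".

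Section 6.4.2, on temporary discontinuation, says: "Abatacept can be temporarily held for a maximum of 2 weeks for significant viral infections or for bacterial infections requiring antibiotics". The next sentence is "Patients may continue/resume study drug at discretion of physician". The section then says that holds for COVID-19 are treated like holds for other viral infections, and adds that "Study drug administration in COVID-19 positive patients will be handled per physician discretion", subject to CDC and American College of Rheumatology (ACR) guidelines.

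Section 6.7, on COVID-19, says: "The re-start of study drug after COVID-19 infection is at the discretion of the PI, following ACR guidance". It refers the reader to sections 4.9 and 6.4.2 for more, but not to the mandatory list in 6.4.

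The same list in 6.4 contains two non-compliance items, one for study drug and one for the weekly diary. The text of each says that participants "may be permanently discontinued from study drug at the discretion of the Site Investigator after consultation with the sponsor".

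**The concern.** Abatacept suppresses part of the immune response, the participants may be as young as 2, and section 6.2 names infection among the most common risks. What happens to dosing after a serious infection is therefore a core safety instruction. It should give the same answer at each of the up to 30 centres named in section 3.1.

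As written, 6.4 gives a site no latitude after a serious infection, while 6.4.2 and 6.7 give latitude for categories of infection that are not limited by severity. Where the categories overlap, one site could stop the drug for good, another could restart it, and each could cite the protocol. Section 11.3 defines a deviation as not conducting the study according to the protocol, so in such a case it would be unclear which of the two sites had deviated. Exposure in the treated group could also differ by site for a reason that nobody planned.

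**Working it through.** No arithmetic decides this point. It rests on whether the provisions agree, so they are set side by side.

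1. **Force of the 6.4 list.** The heading is mandatory and the stop is permanent. The infection item carries no qualifier. The list also has an item for physician discretion, but that adds a reason to stop; it does not soften the infection item.

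2. **Scope of 6.4.2.** The hold covers significant viral infections and bacterial infections needing antibiotics. No route of antibiotic, care setting or upper limit of severity is given. Resumption is at the physician's discretion. Nothing says that infections meeting the 6.4 item are outside the section.

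3. **Scope of the COVID-19 wording.** Section 6.4.2 (dosing in COVID-19 positive patients) and section 6.7 (restart after COVID-19) both leave the decision to discretion under outside guidance. Neither limits that discretion by severity. The decision-maker is the physician in one and the PI in the other.

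4. **Can COVID-19 be serious within this protocol?** Yes. Section 7.1 provides for COVID-19 that meets the SAE criteria, and section 7.6 counts inpatient hospitalisation among those criteria. Section 6.4 does not refer to 7.6, so its term is not formally tied to that definition. It is still hard to see how COVID-19 that is an SAE would not be a serious infection in ordinary usage.

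5. **Overlap.** Take a child admitted to hospital with COVID-19. Under step 1 the drug must be stopped permanently. Under step 3 restart is a matter of judgement. Both provisions apply on their plain wording, and no sentence ranks them. For a child admitted with a bacterial infection treated with antibiotics, steps 1 and 2 overlap in the same way, but less directly, because nothing in 6.4.2 shows that serious bacterial infection was in view.

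6. **Was a severity marker available?** The protocol grades infections elsewhere. Exclusion 19 separates hospitalisation or IV antibiotics from oral antibiotics, and section 7.5 lists infections treated with IV anti-infectives. Sections 6.4 and 6.4.2 use none of these. This shows only that the term was left open; which marker should apply, if any, is for the sponsor.

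7. **Size.** The documents give no rate of serious infection. *Assumption:* 1% to 3% over the dosing period. With 89 enrolled, 0.01 × 89 = 0.9 and 0.03 × 89 = 2.7, so about 1 to 3 children. This counts every serious infection, so at those rates it is an upper bound on the children whose dosing would actually differ. For one such child, the most that can turn on the reading is 24 − 1 = 23 doses, if the infection follows the first dose.

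8. **Effect on the primary comparison.** Section 9.4.2 rests on extension rates of 34.3% and 15%, 80 evaluable participants and 428 registry patients. None of these depends on the infection rule. Sections 6.4 and 6.4.3 keep participants who stop drug in follow-up, and section 9.1 follows ITT principles. Sample size and power do not change.

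9. **Secondary mismatch.** The heading in 6.4 says *must*; the two non-compliance items beneath it say *may*. The text of each item makes the intent fairly clear, but heading and items do not agree.

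**The case against.** The best defence is a tiered reading. Section 6.4.2 sits under 6.4, concerns temporary discontinuation and never uses the word serious. A sensible investigator could take 6.4 to govern serious infections and 6.4.2 to govern lesser ones, with 7.6 supplying the meaning. For infections other than COVID-19 this is plausible, and it is why the bacterial case is put as the less clear one. It does not settle COVID-19, where the discretion in 6.4.2 and 6.7 has no severity limit and 7.1 shows that serious cases were foreseen.

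The COVID-19 discretion is also qualified: it follows CDC and ACR guidance. That stands. The guidance is not part of the documents, so it cannot be seen here whether it treats severe cases separately. A reader might infer that the protocol permits unrestricted re-dosing after any COVID-19 infection; the text does not go that far. But outside guidance does not say how the discretion relates to the protocol's own mandatory stop.

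The item "SAE attributed to abatacept" narrows the gap, because a serious infection attributed to the drug falls under a second mandatory item. It does not help with a serious infection judged unrelated, and 6.4.2 and 6.7 do not refer to that item either.

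Three further inferences are tempting and are not supported:

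- *That the 2-week limit on holds is contradicted for COVID-19.* Section 6.4.2 sets physician discretion beside the limit for infections generally, and 6.7 sends the reader back to 6.4.2. That evidence of conflict is weak.
- *That the DSMB could not interpret the infection data.* Section 7.6 requires SAEs and ESIs to be reported whatever their cause, so the events would still be seen.
- *That the hold around a first COVID-19 vaccine dose makes a child non-compliant.* The protocol does not call a directed hold a missed dose. Whether more than one weekly dose is lost depends on timing, and the consequence named at that threshold is re-education.

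**Conclusion.** The conflict is real. For COVID-19 that is a serious infection, the protocol gives two opposite instructions and does not rank them. For a serious bacterial infection treated with antibiotics the same overlap exists on the wording, but a tiered reading could resolve it. The mismatch between *must* and *may* in the non-compliance items is a minor drafting fault.

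A reader might infer that sites are in fact handling the same case differently. Nothing in the documents shows this; it is a possible consequence of the wording.

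The number of children is probably small: about 1 to 3 of 89 with a serious infection, if the assumed 1% to 3% is near the truth, and fewer whose dosing would differ. For each of them, up to 23 of 24 doses could depend on which section the site reads. The point concerns consistent safety handling and exposure, not the efficacy inference. It should be corrected, and it does not threaten the primary analysis.

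**What to change.** Reconcile sections 6.4, 6.4.2 and 6.7 so that one provision governs serious infections, COVID-19 included. To do that, the sponsor should state:

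- what the infection item in 6.4 means;
- whether the resume provision in 6.4.2 and the restart provision in 6.7 apply to infections that meet it;
- how the CDC and ACR guidance relates to the mandatory list, and who decides, since 6.4.2 names the physician and 6.7 the PI.

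Separately, bring the mandatory heading of 6.4 and the discretionary wording of its two non-compliance items into agreement.

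Which clinical rule should apply is for the sponsor to decide, and none is proposed here. The cost is a protocol clarification and a memo to sites, with no added procedures, visits or participants.

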6.4.1 Procedures for Monitoring Study Drug Compliance

The participant/parent will be given a patient diary (electronic app or paper diary) and will be instructed how and when to use the study drug. The study participant diary will be reviewed at each visit throughout the study to confirm the study participants' compliance with study drug throughout the study. Participants who are non-compliant should be re-educated on the importance of treatment compliance

6.4.2 Temporary Discontinuation of Study Drug

Abatacept can be temporarily held for a maximum of 2 weeks for significant viral infections or for bacterial infections requiring antibiotics. Patients may continue/resume study drug at discretion of physician. Temporary discontinuation of study drug for COVID-19 infection should be handled the same as temporary discontinuations for other viral infections. Study drug administration in COVID-19 positive patients will be handled per physician discretion, following CDC and American College of Rheumatology COVID-19 guidelines. With regards to vaccinations for COVID-19, administration of abatacept will follow the guidance set forth by the American College of Rheumatology to hold SQ abatacept one week prior and one week after the first COVID-19 vaccine dose (only). There is no interruption around the second vaccine dose.⁶⁸

6.4.3 Discontinuation of Study Drug

Study participants may choose to stop taking study drug before the end of the study. A participant may also be asked to stop study drug at the Site Investigator's discretion. Participants who have permanently discontinued study drug are not required to withdraw from the study. Participants who have permanently discontinued study drug and have not withdrawn consent may continue in the study and complete all remaining protocol specified visits.

6.4.4 Study Drug Discontinuation Study Assessments

The site Investigator must make every effort to have the study participant return to the clinic as soon as possible after the participant permanently discontinues study drug to determine if they want to withdraw from the study. If the participant chooses to withdraw from the study every attempt should be made to have all evaluations and procedures as outlined in the Schedule of Events performed. (see Table 2 in Section 4.3.1)

6.4.5 Withdrawal from Study

There are no pre-determined protocol-specific study withdrawal criteria, however, study participants may choose to withdraw from the study at any time and withdraw their consent from further participation in the study. The Site Investigator must document the reason (if specified by the participant) for the withdrawal of consent. Participants who wish to withdraw from further participation in the study should be encouraged to return to the clinic as soon as possible to complete the M12 End of Study Visit. Every attempt should be made to have all evaluations and procedures as outlined in the Schedule of Events performed. (see Table 2 in Section 4.3.1)

